- d. **Recruitment efforts:** The success of our recruiting efforts will be dependent on developing and maintaining collaborative relationships with personnel at clinic sites. The PI has already obtained the support of GCCE Medical Director, Deputy Director, Social Worker, and Administrator. In addition, during the start-up phase of the study, we will make informal presentations about the study to center clinicians and also presentations at formal protocol start-up meetings with clinic personnel. These steps are important to introduce the study, make clinicians and staff more knowledgeable about the objectives, eligibility criteria, and logistics of the study and gain their support. We have devised a process for working with physicians and nurses and other practitioners in the clinic setting that facilitates accrual of patients into clinic studies. A major concern of clinic personnel is disruption in the flow of the clinic. The PI will meet regularly with clinic personnel to cooperate with and adhere to policies for accessing patients and to ensure that our recruiting efforts do not become burdensome for clinical staff. Clinic staff will be asked to assist with identifying patients diagnosed with a recent diagnosis of cancer. We will also review charts to confirm type cancer, stage of cancer, type and duration of planned treatment, and psychological distress screening scores.
- e. **Field Methods:** Research participants will be required to participate in intervention activities and 5 data collection interviews (1 optional open-ended interview). Interviews to complete both open-ended interviews and quantitative measures will take approximately 45 minutes. The actual administration of the intervention (viewing of video recordings) will take approximately 30 minutes with all sessions to occur over a 3-week period.

Participants will be asked to complete interviews at baseline (time of enrollment into study), after each intervention session, and at 6 weeks. These time intervals will allow us

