to identify the factors and strategies that affect health outcomes over time and serve to provide preliminary data to support a larger test of the intervention. These points will also allow for comparisons with other long-term investigations of psychological distress among cancer patients. At baseline data collection we will collect demographic characteristics of participants including age, gender, education, marital status, occupation, employment status, religious affiliation, proximity to family, type and stage of cancer, type treatment, date of diagnosis, date of treatment, and psychological distress screening scores. All data collection will be conducted by phone or video conferencing platform. There will be an 6th optional open-ended interview after the interview sessions to further explore sources of and expressions of distress among participants.

*Demographic and clinical characteristics.* For patients, we will collect data on psychological distress levels (the NCCN Distress score from patient records and the Hospital Anxiety, Depression Scale (HADS)), type and staging of cancer, and type of cancer treatment by either chart review or self-report. For patients and FCGs we will collect information on age, gender, education level, health status, religious affiliation, religiosity, insured status, income, and geographic residence. The religiosity scale measures frequency of using spiritual practices such as the use of religious songs, reading religious materials, and, attending church. Collection of data for demographic and clinical characteristics will occur immediately after obtaining informed consent and before viewing the video narratives.

*NCCN Distress Scale (National Comprehensive Cancer Network)* is a well-known screening tool for distress. In the GCC, this tool is administered to all newly diagnosed cancer patients. This screening tool is a thermometer on which patients rate their distress on a level of 0-10 with 10=extreme distress and 0=no distress. The NCCN-DT will be obtained from patient records to determine eligibility for this study. We will only recruit patients with a NCCN-DT score of  $\geq 4$  which is likely indicative of high levels of distress.

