*Psychological distress* levels for cancer patients will be measured with the Hospital Anxiety, Depression Scale (HADS). The HADS is a 14-item self-report scale for anxiety and depressive states for patients. Internal consistency with African American oncology patients has ranged from .77 (Anxiety) and .78 (Depression). The HADS is sensitive to change after integrative therapy interventions with scores for Anxiety (8.20 $\pm$ 4.34 to 5.79 $\pm$ 3.64); Depression (5.97 $\pm$ 4.00 to 3.96 $\pm$ 3.23). Scoring for the Anxiety and Depression Subscales of the HADS is (0-21); Normal (0-7); Borderline Abnormal Case (8-10); and Abnormal Case (11-21). Patients and family caregivers will be asked to complete this evaluation at baseline and after all of the intervention sessions.

*Quantitative Assessment of narrative quality (narrative characteristics, identification, transportation)*. Assessment of narrative quality (narrative characteristics, identification, and transportation) will be examined using the Narrative Quality Assessment Tool. Narrative characteristics will be examined using a 9 item scale that measures perceived likability of characters in the story, emotional relevance of the storyline, and cultural elements of the stories. Identification will be examined using a 8-item scale that measures the degree to which participants are able to relate to the characters in the video recordings or perceive their story to be similar to their own. Transportation (engagement) will be examined using a 6-item scale

that measures participants emotional connections to the stories in the video recordings. Response options will be on a 5-pt scale and similar to that in other questionnaires in this pilot (1=not at all to 5=quite a bit). Internal consistency for the three scales range from .92 - .95 respectively. Validity was determined through hypothesized factor structures (CFA). Patients and family caregivers will be asked to complete these evaluations after each intervention session.

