Qualitative exploration of usability and transportation will occur after each weekly intervention session. During the qualitative assessments, participants will be asked to express their thoughts, feelings, and opinions of the narrators and describe perceptions of similarity to, identification with narrators in the recordings, and, transportation (engagement) of participants to selected recordings. *Participants and FCG's will also be asked to describe ways in which they might use the strategies from the video recordings to cope with their own cancer experience.* Guided by Transportation Theory, the final selection of recordings will consist of those with higher levels of narrative quality. These stories from actual patients and FCG's and used in this intervention are hypothesized to be relatable and acceptable in content and context. In previous storytelling interventions among African American and Latino populations, *listening* to culturally relevant stories resulted in changes in attitudes and behavior change. We will qualitatively assess usability through perceived navigation (ease of use); content (video length, topics covered, presentation); persuasiveness (mood, encouragement); and, value (time spent, future use, potential recommendations to others). **Description of Intervention:** The intervention will consist of participants viewing a selection of video recorded vignettes during 3 weekly sessions. There will be 5 vignettes included in each session with each vignette edited to a real time of 3-4 minutes (each session is 30 minutes). Since the intervention is designed to be self-administered, there will be a video recorded introduction and instructions for use narrated by the PI. The vignettes are of actual African American cancer survivors narrating stories of ways in which hymns can be used to overcome their *anxieties and depressed moods through the use of a hymn. The hymns included represent exemplars from the 5 themes prevalent in the PI's previous research (see Table 2)*.

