**6. Potential Risks/Discomforts to Study Participants and measures to prevent occurrence:**

- a. The risks for injury or bodily harm are minimal since the topics to be discussed are those that typically occur during day to day interactions among family and friends and community (faith-based) groups. A similar study in a southern population has been previously conducted with no known medical risks. Some participants were tearful during their interviews when talking about their illness experience and the support that gave them strength and comfort when anxious or sad but they did not want to stop the interview. Many participants reported that the interview permitted them to discuss a stressful life event they had previously not shared with anyone else.
- b. A select number of participants will be asked to contribute their stories to be included in the larger test of the intervention. Participants that agree to share their stories will be informed of the nature of any disclosure of their illness and other aspects of their stories. Stories from interviews with participants concerned about employment/future employment, reputation, or financial standing will be kept confidential.
- c. Risks that would be associated with loss of privacy or breach of confidentiality. Participants will be informed that it may be possible for others to identify them should their stories be used in a future research study. However, any names, addresses or statements to identify third parties mentioned will be deleted.
- d. Steps taken to minimize the risks. This research consists of a preliminary study to test the feasibility and acceptability of an intervention using hymns to alleviate psychological distress. Discussions of favorite hymn used in response to stressful life events are a frequent part of public conversations among African Americans. Persons who become increasingly distressed or emotionally upset during the interviews will be encouraged to contact their physician for referral to mental health counseling. Efforts will be made to minimize respondent burden during the interview. The PI is sensitive to verbal and nonverbal expressions of fatigue such as squirming, looking around, gazing out the window or simply stating they are too tired to finish. Participants who say they are too tired or are otherwise not able to complete the interview once started, will be given the option of withdrawing or rescheduling their appointment.

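### HADS is not explicitly scheduled for participants who stop viewing the videos, nor named at the 6-week interview, so the distress effect size risks reflecting those who keep attending

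*Combined protocol and SAP*

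**What the plan says.** Section 1 (Study Design) makes psychological distress the primary outcome and effect-size estimation an aim. Section 2.c says those effect sizes will inform the power calculation of a later RCT.

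The collection schedule is spread over several paragraphs of section 2:

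- **HADS:** "Patients and family caregivers will be asked to complete this evaluation at baseline and after all of the intervention sessions".
- **Narrative-quality scales:** "Patients and family caregivers will be asked to complete these evaluations after each intervention session".
- **Usability and transportation interviews:** "Qualitative exploration of usability and transportation will occur after each weekly intervention session".
- **All interviews (2.e, Field Methods):** "Participants will be asked to complete interviews at baseline (time of enrollment into study), after each intervention session, and at 6 weeks". On their content: "Interviews to complete both open-ended interviews and quantitative measures will take approximately 45 minutes". The text then says that these times allow outcomes to be followed and compared with longer-term research on distress. It assigns no instrument to the 6-week interview.
- **A sixth contact:** an "optional open-ended interview after the interview sessions to further explore sources of and expressions of distress among participants".

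On staying in the study, 2.e states: "Research participants will be required to participate in intervention activities and 5 data collection interviews". Section 2.b makes willingness to take part in every study activity an inclusion criterion. Section 6.d says that a participant too tired or otherwise unable to finish an interview "will be given the option of withdrawing or rescheduling their appointment".

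Under Aim 2 (section C), acceptability is judged by enrollment and participation as well as by Transportation Theory concepts. Section 10 gives no analysis of HADS change, no analysis set and no rule for missing data.

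**The concern.** Consider someone who views session 1 and then stops, whether from dislike, fatigue or illness. Session 1 is assessed. Whether a HADS is due after that depends on how one sentence is read and on what the 6-week interview contains. No contact is written for asking why the person stopped.

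People who stop are informative about acceptability, and they may differ in distress from those who continue. If their later HADS is not collected, the pre-post change rests on those who stayed, and the likely direction is favourable. That change is meant to size an RCT, so an inflated value would make the later trial too small. An analysis written afterwards cannot recover data that were never collected.

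The ratings have a smaller version of the same problem. Section 10 keeps the top 50% of narratives by rank. If different vignettes are shown in different sessions, which the text does not state, the later ones are rated only by people still viewing.

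**Working it through.** **1. Count of contacts.** One baseline interview, three post-session interviews and one at 6 weeks give 1 + 3 + 1 = 5, which reproduces the plan's five. Adding the optional interview gives 6, and section 8 agrees: $180 / $30 = 6. Of the four required post-baseline contacts, three are tied to a session and one (6 weeks) to the calendar.

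**2. What each participant supplies after baseline, by sessions viewed.** This takes the schedule as linked to viewing. Reading A is HADS after each session; reading B is HADS once, after the last session.

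| Sessions viewed | HADS, reading A | HADS, reading B | Rating and usability occasions | 6-week interview |
|---|---|---|---|---|
| 0 | 0 | 0 | 0 | due, instruments not named |
| 1 | 1 | 0 | 1 | due, instruments not named |
| 2 | 2 | 0 | 2 | due, instruments not named |
| 3 | 3 | 1 | 3 | due, instruments not named |

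Under A, a stopper who viewed at least one session gives some HADS but none later. Under B, only someone who viewed all three sessions gives a post-baseline HADS, unless the 6-week interview includes it. Under both, partial attenders contribute ratings and usability data.

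**3. Possible size (illustration only).** The documents give no stopping rate. The HADS paragraph cites an anxiety change after integrative therapy, a different intervention, of 8.20 to 5.79 with baseline SD 4.34.

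- Change in those who continue: 8.20 − 5.79 = 2.41 points; 2.41 / 4.34 = 0.56 SD.
- Assume a fraction f stops and stoppers change by zero. The all-enrolled change is 2.41 × (1 − f), and the overstatement is 1/(1 − f) − 1.
- At a fixed SD, required sample size varies as 1/d², so planning on the continuers' figure understates the later trial by a factor of 1/(1 − f)².

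| f (assumed) | All-enrolled change | In SD | Overstatement | Sample-size factor |
|---|---|---|---|---|
| 10% | 2.17 | 0.50 | 11% | 1.23 |
| 20% | 1.93 | 0.44 | 25% | 1.56 |
| 30% | 1.69 | 0.39 | 43% | 2.04 |

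**4. Sensitivity to the zero-change assumption.** If stoppers change by a proportion r of the continuers' change, the overstatement is 1/(1 − f(1 − r)) − 1. With r = 0.5 it is 1/0.95 − 1 = 5%, 1/0.90 − 1 = 11% and 1/0.85 − 1 = 18% for the same three values of f. With r = 1 it is zero.

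The only design calculation in the plan (2.c: 80% power, 40 dyads) states no dropout allowance. This point does not depend on it.

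**The case against.** A reader might infer that acceptability and HADS change will describe completers only. The documents do not support that, for these reasons:

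- Ratings and usability are collected after each session, so someone who views one session and dislikes it is heard on that session.
- Participation is part of the definition of acceptability, and counting it covers people who stop.
- The HADS sentence can mean after each session. It can also give only a time, the close of the 3-week period, with no condition that every session was viewed.
- It is tempting to call the 6-week interview empty. Field Methods describes interviews in general as including quantitative measures and links the listed times to distress research, so its content is unspecified rather than absent.
- The optional sixth interview also concerns distress and is not tied to viewing a particular session.
- Section 6.d concerns an unfinished interview, not the videos. Rescheduling keeps the person in, and withdrawing may mean only from that appointment.
- Consent pages were not in the text reviewed and may address partial participation.

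All of this stands, and it rules out the stronger claim. What remains is narrower. The text does not name HADS at 6 weeks and does not say what is collected from someone who has stopped viewing. The optional interview is open-ended and secures no HADS score. Participation counts show that people stopped, not why, and section 10 plans no analysis of them.

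It is also fair to say that the missing HADS change analysis in section 10 is the larger gap. Filling it would not supply scores that were never taken.

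**Conclusion.** The concern holds in limited form. Followed as written, the plan need not obtain a later HADS, or a reason, from a participant who stops viewing. The HADS effect size and the ratings of any later sessions therefore risk leaning towards continuing attenders. The likely direction is favourable, on the assumption that stoppers do less well.

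The size is unknown. The 11% to 43% range is not an estimate for this study: it rests on assumed stopping of 10% to 30%, zero change in stoppers, and an effect size reported only for those who continue, which section 10 neither specifies nor excludes. If stoppers change as much as the others, there is no bias. The change is worth making because it is cheap and the effect size is intended to size a later trial.

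**What to change.** 1. In Field Methods (2.e) and the HADS paragraph, schedule HADS at the end of the 3-week period and at the 6-week interview for every enrolled patient and caregiver, regardless of sessions viewed. State whether it is also taken after each session.
2. Define stopping the sessions separately from withdrawing from data collection. In 6.d, add that a participant may end one interview and remain for later ones.
3. When someone stops viewing, record the reason once, by phone.
4. In section 10, report HADS change and session attendance with all enrolled as the denominator and completers as a secondary view. State how missing HADS scores are handled.

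The cost is mainly wording. Data collection is already by phone or video, the 6-week contact already exists, and no new instrument is needed. The downside is a few extra short calls and estimates that may look less favourable.

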**6. Potential Risks/Discomforts to Study Participants and measures to prevent occurrence:**

- a. The risks for injury or bodily harm are minimal since the topics to be discussed are those that typically occur during day to day interactions among family and friends and community (faith-based) groups. A similar study in a southern population has been previously conducted with no known medical risks. Some participants were tearful during their interviews when talking about their illness experience and the support that gave them strength and comfort when anxious or sad but they did not want to stop the interview. Many participants reported that the interview permitted them to discuss a stressful life event they had previously not shared with anyone else.
- b. A select number of participants will be asked to contribute their stories to be included in the larger test of the intervention. Participants that agree to share their stories will be informed of the nature of any disclosure of their illness and other aspects of their stories. Stories from interviews with participants concerned about employment/future employment, reputation, or financial standing will be kept confidential.
- c. Risks that would be associated with loss of privacy or breach of confidentiality. Participants will be informed that it may be possible for others to identify them should their stories be used in a future research study. However, any names, addresses or statements to identify third parties mentioned will be deleted.
- d. Steps taken to minimize the risks. This research consists of a preliminary study to test the feasibility and acceptability of an intervention using hymns to alleviate psychological distress. Discussions of favorite hymn used in response to stressful life events are a frequent part of public conversations among African Americans. Persons who become increasingly distressed or emotionally upset during the interviews will be encouraged to contact their physician for referral to mental health counseling. Efforts will be made to minimize respondent burden during the interview. The PI is sensitive to verbal and nonverbal expressions of fatigue such as squirming, looking around, gazing out the window or simply stating they are too tired to finish. Participants who say they are too tired or are otherwise not able to complete the interview once started, will be given the option of withdrawing or rescheduling their appointment.

**7. Benefits:** One potential benefit to individuals participating in the study is that respondents may receive comfort and/or spiritual uplifting and seek the support of others after viewing these narratives that include religious based songs and text. No other direct benefits to individual participants are likely. The benefit to health services practitioners, on the other hand, is great. Acknowledging, documenting, and describing the nature of religious based songs that help comfort older African Americans through times of adversity will facilitate the development of intervention strategies specific to African Americans but also likely in other cancer populations attempting to cope with chronic illness and/or life-threatening disease. Effective intervention strategies, in turn, will improve the overall well-being of individuals living with such illnesses.

**8. Compensation for time and effort:** Participants will be given \$30 for each completed interview not to exceed \$180.

**9. Data Analysis: Data Management and Monitoring:**

- a. To maintain confidentiality of the data, each participant will be assigned a subject identification number. The subject identification number will be used to keep track of recorded interviews and transcribed data. Identifying information associated with the

subject identification numbers will be kept separate from the data at all times. Digitally – recorded interviews and hard copies of transcribed interviews will be kept on a password protected computer. Data files of transcribed interviews and a database with the research participants' information will be kept on a secure server that can only be accessed by authorized personnel with valid user id and password.

- b.** *The PI and RA will complete research training on responsible conduct of research (RCR) using the Collaborative Institutional Training Initiative (CITI). Data and back-up data (study and PHI) will be maintained in separate databases on the team's password-protected database and server as described above. Data will be entered via (Research Electronic Data Capture (REDCap)), a secure web-based application that supports data capture and management for research studies. REDCap data entry also assists in efficient project management and data analysis. Demographic data will also be entered into the Winship Oncore System. Data collected from open-ended interviews will be audio recorded and transcribed and checked for accuracy. All audio-recorded interviews will be immediately uploaded onto a password protected computer for later transcription and analysis. Interviews will be deleted from audio recording devices once data is uploaded onto password protected computers. Interview data will be maintained on password protected computers.*

